### **8.2.1.3 Proportion of patients with normalization of biochemical measures of disease activity**

This analysis will be done for serum cortisol, serum cortisol after dexamethasone, salivary cortisol, ACTH.

For each time window, the number and percentage of patients with normalization of biochemical measures of disease activity will be presented together with corresponding exact

(Clopper-Pearson) 95% CI. For this analysis, a patient is considered to have achieved normalization within a time window if all measurements taken within this window are within the normal range. The proportion will be calculated relative to the number of patients with a value for the respective time point.

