3.5 Visit schedule and assessments

This study is observational in nature and does not impose a therapy protocol, diagnostic/therapeutic interventions or a visit schedule. However, in order to help encourage more uniform data collection across study sites and patients a suggested schedule of assessments has been provided in [Table 3-1](#).

Patients will be treated with pasireotide s.c. according to the investigator's judgment and in accordance with the local (country-specific) pasireotide s.c. prescribing information. Available data will be collected at patients' visits to their site.

Table 3-1 Suggested schedule of assessments

Visit/Frequency	Baseline	Monthly	Every 3 months	Every 6 months	Every 12 months	End of Treatment	End Of study
Informed Consent	x						
Demography	x						
Inclusion/Exclusion Criteria	x						
Relevant medical history/Current medical conditions (history of smoking, history of alcohol use, presence of hepatitis B and C infections)	x						
Cushing's disease history	x						
Prior medications - For Cushing's Disease	x						
Coagulation test (Prothrombin time, APTT)	x					x	x
Vital Signs	x	x	x	x	x	x	x
Pregnancy test	x	x	x	x	x	x	x
Clinical symptoms of Cushing's disease	x		x			x	x
Glycemic status, FPG	x ¹	x ²				x ³	x ³
Glycemic status, HbA1c	x ¹		x			x ⁴	x ⁴
Salivary cortisol	x	x ⁵	x			x	x
Serum cortisol after dexamethasone	x	x ⁵	x			x	x
24 hour urine collection - Urinary free cortisol	x	x ⁵	x			x	x
Pituitary imaging local analysis (MRI/CT scan)	x				x	x	x
LFTs (ALT, AST, Alkaline phosphatase)	x ¹	x ⁶	x			x	x
12 lead ECG evaluation - local analysis	x ^{1,7}		x			x	x
Hematology/Blood Chemistry *	x			x		x	x
Thyroid function tests (TSH, Free T4)	x				x	x	x
Gallbladder imaging	x ¹			x	x	x	x
Cushing's syndrome QoL/ Euro QoL-5D health QoL/ Patient Reported outcome (PRO)	x			x		x	x

Visit/Frequency	Baseline	Monthly	Every 3 months	Every 6 months	Every 12 months	End of Treatment	End Of study
Dose Administration Record-Pasireotide s.c	x	At each visit				x	x
Adverse Events	x	At each visit				x	x
Concomitant Medication	x	At each visit				x	x

¹ prior starting treatment with pasireotide s.c
² self-monitoring of blood glucose and/or FPG every week for the 1st two to three months and periodically thereafter, as clinically appropriate.
³ Monitoring of FPG 4 weeks after the end of treatment
⁴ Monitoring of HbA1c 3 months after the end of treatment
⁵ every month for the first 3 month and then every 3 months

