⁶ Monitoring of liver function after one, two, four, eight and twelve weeks
⁷ one week after start of treatment, QTcF/QTcB prolongations > 480 msec have to be reported as adverse events
* **Hematology:** WBC, RBC, Hemoglobin, Hematocrit, Platelets, Neutrophils, Lymphocytes, Eosinophils, Basophils, Monocytes
Blood chemistry: γGT, α-amylase, Total bilirubin, Indirect bilirubin, Direct bilirubin, Sodium, Potassium, Magnesium, GH, IGF-1, PT, Plasma ACTH, Triglyceride, Cholesterol, LDL, HDL

Recommended assessments are specified and listed in the local product label.

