### 6.1.7 Time windows

There is no visit schedule and no planned assessment in this non-interventional study. Assessment related data are collected as they become available during the study period. Therefore assessments are assigned to time windows based on the study day on which the assessment is performed. For mean UFC, the sample day of the first urine sample included in the calculation of mean UFC will be used for assignment to time windows.

If there are multiple values within a time window, the assessment closest to the target day of the time window will be used, if not indicated otherwise. If two assessments are equally close (e.g. 7 days before and 7 days after target day), the later will be used.

Time windows will be assigned according to the window schema in Table 6-2 if assessments are expected more frequently than every 6 months. Otherwise the time windows in Table 6-3 will be applied (e.g., for tumor volume, variables related to patient reported outcome questionnaires, findings of gallbladder ultrasound).

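### The all-values-normal rule for biochemical normalization gets harder to meet as windows hold more values, so later windows can show a lower rate with unchanged disease control

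*SAP*

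**What the plan says.** SAP 8.2.1.3 defines the endpoint: a patient has achieved normalization in a window "if all measurements taken within this window are within the normal range". On the denominator it says: "The proportion will be calculated relative to the number of patients with a value for the respective time point". The number of values a patient contributes plays no part. On scope: "This analysis will be done for serum cortisol, serum cortisol after dexamethasone, salivary cortisol, ACTH".

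The general rule in SAP 6.1.7 for several values in one window is that "the assessment closest to the target day of the time window will be used, if not indicated otherwise". Section 8.2.1.3 uses that proviso and gives no reason. Protocol 6.5.1.4 asks for the proportion per visit window and sets no within-window rule.

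On testing frequency, Protocol 3.5 imposes no visit schedule, although "a suggested schedule of assessments has been provided in" Table 3-1. For salivary cortisol and serum cortisol after dexamethasone, footnote 5 of that table reads "every month for the first 3 month and then every 3 months". ACTH is in the blood chemistry panel ("GH, IGF-1, PT, Plasma ACTH, Triglyceride, Cholesterol, LDL, HDL"), whose row is marked every 6 months. Basal serum cortisol has no row.

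**The concern.** A rule that every value must be normal is a reasonable strict definition if it is equally strict wherever it is applied. Here it is not. A patient with one value in a window has one hurdle to clear, and a patient with three has three. Two comparisons suffer:

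- **Between windows.** Windows from Month 18 on are about twice as wide as those at Months 6 and 9. Under regular testing they tend to hold more values, so the proportion falls even if control is constant.
- **Between patients.** Patients tested more often are less likely to qualify. Protocol 3.5.3.1 expects UFC testing to be more frequent before control is reached than after. If the same holds for these analytes, test count is tied to disease status.

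The endpoint is normalization over time in a study meant to document long-term efficacy. An artificial decline after the first year would look like loss of biochemical control, and nothing in the planned table would let a reader tell the two apart.

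**Working it through.** The documents give no expected normalization rate, so there is no planned figure to reproduce. The check is how many values fall in each window and what the rule then does to a constant rate.

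**1. Window widths** (Table 6-2, end day − start day + 1): Month 6, 229−137+1 = 93; Month 9, 91; Month 12, 138; Month 18, 183; Month 24, 180; Month 30, 184; Month 36, 182 days.

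**2. Nominal test days.** Footnote 5 gives Months 1, 2, 3, 6, 9, …, 36. At 30.4375 days per month these are days 30, 61, 91, 183, 274, 365, 457, 548, 639, 731, 822, 913, 1004 and 1096. Values per window: Month 1, 1; Month 3, 2; Month 6, 1; Month 9, 1; Month 12, 2; Month 18, 2; Month 24, 1; Month 30, 3; Month 36, 1.

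Several of these days sit on a window edge: 457 (Month 12 ends on 458), 639 (Month 18 ends on 641), 822 (the first day of Month 30) and 1004 (Month 30 ends on 1005). With 90- or 91-day spacing, Months 18, 24 and 30 hold 2 each. The nominal counts for single late windows are therefore fragile.

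**3. Timing variation.** Let each test move uniformly by ±14 days (assumption). For Month 18:
- The Month 18 test (nominal day 548) always counts.
- The Month 15 test (456.6) enters if it lands at 458.5 or later: (14 − 1.9)/28 ≈ 0.43.
- The Month 21 test (639.2) stays if it lands before 641.5: (14 + 2.3)/28 ≈ 0.58.

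The mean is 1 + 0.43 + 0.58 = 2.01. The chances of 1, 2 and 3 values are about 0.24, 0.51 and 0.25. The same steps give mean counts of 1.0 at Months 6 and 9, 1.57 at Month 12, 1.90 at Month 24, 2.06 at Month 30 and 1.46 at Month 36. Months 1 and 3 average about 1.5, because of the early monthly tests.

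**4. Chance that all k values are normal.** If p is the chance that one value is normal, independence gives p^k. With within-patient correlation ρ, a one-factor normal threshold model gives ∫ Φ((z_p − √ρ·x)/√(1−ρ))^k φ(x) dx. For p = 0.70:

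| ρ | 1 value | 2 values | 3 values |
|---|---|---|---|
| 0 | 70% | 49.0% | 34.3% |
| 0.5 | 70% | 55.7% | 47.0% |
| 0.7 | 70% | 59.1% | 52.7% |
| 0.9 | 70% | 63.8% | 60.4% |
| 1 | 70% | 70% | 70% |

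**5. Expected reported rate, p = 0.70, ±14 days.** Month 18 at ρ = 0: 0.24×70 + 0.51×49 + 0.25×34.3 ≈ 50%. In the same way:

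| Window | ρ = 0 | 0.5 | 0.7 | 0.9 |
|---|---|---|---|---|
| Months 6, 9 | 70% | 70% | 70% | 70% |
| Month 12 | 58% | 62% | 64% | 66% |
| Month 18 | 50% | 57% | 60% | 64% |
| Month 24 | 52% | 58% | 61% | 65% |
| Month 30 | 50% | 56% | 60% | 64% |
| Month 36 | 60% | 63% | 65% | 67% |

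For p = 0.90 the rate is 90% at Months 6 and 9. At Months 18 to 30 it is about 81–82% (ρ = 0) to 87% (ρ = 0.9), a drop of about 3 to 9 points.

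**6. One value per window.** Under the closest-to-target rule the expected rate is p in every window, whatever the width or the count.

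**7. Other analytes.** Six-monthly ACTH puts 0 or 1 value in each window, so the suggested schedule produces no drop. Basal serum cortisol cannot be assessed from the documents.

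**The case against.** The best defence is that the rule is a deliberate choice. Section 6.1.7 allows exceptions, 8.2.1.3 makes one, and the protocol is not contradicted. Requiring all values to be normal avoids declaring control on one favourable sample. The same four analytes are also summarized per window as observed values, changes from baseline and box-plots (SAP 8.2.1.2), and through a mixed model (SAP 8.2.1). The endpoint is secondary, and no hypothesis is tested.

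Much of this stands. The strict rule has clinical sense and is worth keeping in the report, and no error rate or sample size is touched. But the planned time courses describe continuous levels and do not correct the proportion. The sensitivity analyses in SAP 8.2.1 also cover continuous parameters only.

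Some stronger readings are tempting but not supported:

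- A reader might infer a large swing between Month 24 (one value) and Month 30 (three). That is an edge effect of exact calendar dates. It disappears with 90- or 91-day spacing, and with ±14 days both windows average about two.
- A reader might count two values at Month 36 by adding a test at Month 39 (day 1187). Follow-up is 3 years, and the nominal count is one.
- A reader might take width itself as the cause. Months 24, 30 and 36 are almost equally wide. The number of values drives the effect, and width matters only by raising the usual number.
- A reader might treat the tests as scheduled, or the effect as shown for all four analytes. Table 3-1 is only suggested, and it implies repeat values within a window for two of them.

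**Conclusion.** The point holds in a limited form. As written, the rule lowers the expected normalization rate in windows with more values unless a patient's values within a window always agree. For salivary and post-dexamethasone cortisol under the suggested schedule, the lasting contrast is Months 6 and 9 (about one value) against Months 18 to 30 (about two), with Months 12 and 36 between. At an assumed constant 70% per value, the artificial drop is about 18 to 20 points if values are independent, 12 to 14 at correlation 0.5 and 5 to 6 at correlation 0.9.

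The direction follows from the rule and the counts. The size rests on an assumed per-value probability, correlation and timing spread, none of which the documents give. Actual counts will follow local practice and may differ, and extra tests could bring the same distortion to ACTH and basal serum cortisol. Severity is minor to moderate.

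**What to change.** Amend SAP 8.2.1.3 as follows:

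1. In each window, classify normalization on the value closest to the target day, with the 6.1.7 tie rule, preferably as the main row.
2. Keep the all-values version as a second, labelled row, so the stricter result remains available.
3. For each analyte and window, show the number of values per patient (for example, patients with 1, 2, and 3 or more values, and the median).
4. State that the all-values row should not be compared across windows without those counts.

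The cost is SAP wording and an extra row plus counts in existing tables. No new data are needed, and the denominator is unchanged.

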#### *8.2.1.4 Absolute and percentage change from baseline in clinical signs and symptoms*

For each time window, the absolute and percentage change from baseline in clinical signs and symptoms (blood pressure, body weight, body mass index, waist circumference) will be summarized with descriptive statistics. Distribution-free 95% CIs will be given for the median changes.

In addition, the absolute and percentage change from the last assessment while on pasireotide s.c. to the last value during the 90-days follow-up period will be summarized in a similar manner.

#### *8.2.1.5 Proportion of patients with favorable shift from baseline in clinical symptoms of Cushing's disease*

The clinical symptoms of Cushing's disease (facial rubor, striae, bruising, supraclavicular fat pad, dorsal fat pad) are assessed on a 4-point scale ranging from 0 (none) to 3 (severe). A favorable shift corresponds to a decrease on this scale.

For each clinical symptom of Cushing's disease, the change in clinical symptoms will be analyzed using shift tables: for each time point, the post-baseline result will be cross-tabulated against the baseline result. The number and percentage of patients with a favorable shift from baseline to each time window will be presented together with corresponding exact (Clopper-Pearson) 95% CI.

#### *8.2.1.6 Absolute and percentage change from baseline in tumor size*

For time windows Month 6, 12, 18, 24, 30, and 36, absolute and percentage change from baseline in tumor volume will be summarized with descriptive statistics. Distribution-free 95% CIs will be given for the median changes. This summary will only include post-baseline evaluations for which the same method of evaluation (CT scan or MRI) as at baseline.

In addition, the absolute and percentage change from the last assessment while on pasireotide

s.c. to the last value during the 90 days after drug discontinuation will be summarized in a similar manner.

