#### 8.1.2 Statistical hypothesis, model, and method of analysis

The sample size for this study is not based on statistical considerations. It is anticipated that up to approximately 100 sites in about 35 countries will participate in the study. The study will enroll a minimum of 100 patients up to a maximum of 200 patients. The actual sample size may differ from this planned number.

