### **8.2.1.2 Absolute and percentage change from baseline in biochemical measures of disease activity**

For each time window (Month 1, 3, 6, 9, 12, 18, 24, 30, 36), observed values and, the absolute and percentage change from baseline in biochemical measures of disease activity (mean UFC, serum cortisol, serum cortisol after dexamethasone, salivary cortisol, ACTH, fasting serum lipid profile (total cholesterol, HDL, LDL) will be summarized with descriptive statistics. Distribution-free 95% CIs will be given for the median changes.

Furthermore, the time course of these parameters will be displayed graphically using box-plots.

In addition, the absolute and percentage change from the last assessment while on pasireotide s.c. to the last value during the 90-days follow-up period will be summarized in a similar manner.

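### Tumor volume is analysed in six 6-monthly windows although imaging is suggested only yearly, so about half of the patient-windows are empty by design

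*SAP*

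**What the plan says.** **Imaging frequency.** In Protocol 3.5, Table 3-1, the row that begins "Pituitary imaging local analysis (MRI/CT scan" is marked at Baseline, Every 12 months, End of Treatment and End of study. Its monthly, 3-monthly and 6-monthly columns are blank. The table is not binding: the protocol says that "a suggested schedule of assessments has been provided in" Table 3-1 to encourage uniform data collection, and it imposes no visit schedule.

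**Reporting windows.** SAP 8.2.1.6 gives descriptive statistics "For time windows Month 6, 12, 18, 24, 30, and 36, absolute and percentage change from baseline in tumor volume". Table 6-3 sets the limits: Month 6 = Days 137-320, Month 12 = 321-458, Month 18 = 459-641, Month 24 = 642-821, Month 30 = 822-1005, Month 36 = 1006-1187.

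**Choice of table.** SAP 6.1.7 states: "Time windows will be assigned according to the window schema in Table 6-2 if assessments are expected more frequently than every 6 months". Everything else goes to Table 6-3. No annual scheme exists.

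**Analyses that use the windows.** SAP 8.2.1 names tumor size among the variables for the mixed model. SAP 6.2.3 fits that model with window as a class effect and an unstructured covariance. SAP 8.2.1 adds two sensitivity analyses for the continuous efficacy parameters, both with the same model. One imputes the worst value where a window is missing. The other keeps only patients with every value present.

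**The concern.** The window grid is twice as fine as the suggested imaging frequency. A patient imaged as Table 3-1 suggests will miss about every second window without having missed any scan.

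Three analyses are affected:

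- **By-window summary.** Neighbouring columns describe largely different patients, so reading across the columns is not reading change within patients.
- **Mixed model.** The covariances between neighbouring windows have little or no direct support in the data.
- **Sensitivity analyses.** They treat a window in which no scan was due as missing data. One then has almost nobody left. The other fills the gaps with worst values, which, if worst means largest, would pull the results towards growth that nobody measured.

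Change in tumor size over time is a secondary objective (Protocol 2.2), and tumor expansion is listed as an important potential risk (Protocol 3.5.2.3).

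**Working it through.** The documents give no expected number of scans per window, so there is no planned figure to reproduce. The check places yearly scans in the SAP's own windows.

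**Inputs.** Window limits and target days come from SAP Table 6-3, the month length of 30.4375 days from its footnote, and the yearly interval from Protocol Table 3-1. SAP 6.1.6 takes as baseline the last scan on or before first dose, with no look-back limit. For cohort 2, Table 6-1 also allows a baseline scan up to 6 months after first dose. Scan scatter and the age of the baseline scan are not in the documents and are assumed below.

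**Step 1: scans counted from first dose.** 12, 24 and 36 × 30.4375 = 365, 731 and 1096 (rounded). These fall in Months 12, 24 and 36. None falls in Months 6, 18 or 30, so 3 of 6 windows (50%) are empty.

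**Step 2: scans counted from another baseline date.** Adding 365 days repeatedly gives:

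| Baseline scan | Scan days | Windows filled |
|---|---|---|
| 60 days before first dose | 305, 670, 1035 | Months 6, 24, 36 |
| 150 days before first dose | 215, 580, 945 | Months 6, 18, 30 |
| Day 120 (cohort 2) | 485, 850, 1215 | Months 18, 30 (the third is after Month 36) |

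Which windows are filled depends on the baseline date. The number filled stays at three or fewer. The patient in step 1 and the patient with the 150-day-old baseline share no window at all.

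**Step 3: neighbouring windows.** To fill two neighbouring windows, two scans can be at most this far apart (end of the later window minus start of the earlier one):

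- Months 6 and 12: 458 − 137 = 321 days
- Months 12 and 18: 641 − 321 = 320 days
- Months 18 and 24: 821 − 459 = 362 days
- Months 24 and 30: 1005 − 642 = 363 days
- Months 30 and 36: 1187 − 822 = 365 days

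Scans exactly a year apart therefore cannot fill both, apart from the limiting case of Days 822 and 1187. With irregular timing some patients will, but only when the interval is shortened or the scans sit at the outer edges of the pair.

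**Step 4: share of empty patient-windows, by illustration (no dropout).** The figures are percentages of patients with a scan in Months 6, 12, 18, 24, 30 and 36.

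| Assumed baseline scan age, scatter SD | Percent with a scan | Mean filled | Empty |
|---|---|---|---|
| 0-6 months, 0 days | 74.9, 25.1, 50.6, 49.4, 50.0, 50.0 | 300.0/6 = 50.0% | 50.0% |
| 0-6 months, 60 days | 66.9, 29.1, 50.5, 49.1, 50.2, 49.6 | 295.4/6 = 49.2% | 50.8% |
| taken at first dose, 60 days | 22.1, 71.6, 12.4, 86.8, 12.8, 87.0 | 292.7/6 = 48.8% | 51.2% |

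Across variants with baseline scans 0-6 months old and scatter SD 15 to 60 days, the empty share stays within about 50 to 55%. In every scenario 0% of patients fill all six windows.

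**Step 5: covariance.** An unstructured matrix for six windows has 6 × 7 / 2 = 21 parameters. Of its 15 covariances, 5 belong to neighbouring pairs, the ones that step 3 leaves with few or no patients. Three windows need 3 × 4 / 2 = 6 parameters.

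**Step 6: annual windows.** The midpoint rule in the Table 6-3 footnote, applied to targets 365, 731 and 1096 with baseline at Day 1, gives (1 + 365)/2 = 183, (365 + 731)/2 = 548 and (731 + 1096)/2 = 913.5. The windows are Days 183-548, 549-913 and 914-1187, keeping the table's present end day. The first two patients in step 2 and the patient in step 1 now fill all three windows; the cohort 2 patient fills two. Under the assumptions behind the 50 to 55% range, about 0 to 13% of patient-windows are empty.

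**Side observation.** The midpoint rule applied to Table 6-3's own targets gives about Days 92-274 for Month 6, not 137-320; the stated limits fit the Month 3 and Month 9 neighbours of Table 6-2. A scan on Day 320 is 45 days before the Month 12 target and 137 days after the Month 6 target, yet it is labelled Month 6.

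**The case against.** The study is non-interventional. Table 3-1 is a suggestion, and SAP 6.1.7 says there is no planned assessment, with data taken as they arise. Windows finer than a suggested frequency are a normal choice for irregular data, the analysis is descriptive, and counts of patients and missing values are to be reported, so thin columns will be visible. All of this is true. It does not rescue the sensitivity analyses, which convert a scan that was not due into missing data. Nor does it supply another expected imaging frequency: Table 3-1 is the only one given.

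Annual windows also have a real weakness. A scan on Day 200 in a patient who stops then would be labelled Month 12 beside routine scans near Day 365. Flagging such scans makes this visible but does not remove it.

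Three stronger readings are tempting, and the documents do not support them:

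- **Months 6, 18 and 30 hold only off-schedule or stopping scans.** Step 2 shows routine yearly scans landing there when the baseline scan is older, or post-dose in cohort 2.
- **The trend contrasts selected patients with routinely followed ones.** End of Treatment and clinically prompted scans can fall in any window. Month windows take efficacy scans only up to about 3 days after last dose. Nothing in the documents says what prompts a scan, and the mixed model reduces the problem if data are missing at random.
- **ACTH and lipids have the same fault.** SAP 8.2.1.2 does report them "For each time window (Month 1, 3, 6, 9, 12, 18, 24, 30, 36), observed values", while Table 3-1 puts "GH, IGF-1, PT, Plasma ACTH, Triglyceride, Cholesterol, LDL, HDL" in the 6-monthly "Hematology/Blood Chemistry" row. But SAP 6.1.7 does not tie expected frequency to Table 3-1. Table 6-3's month windows start at Day 137, so moving these variables there would take early results out of the by-window summary. No bias is shown for blood samples.

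**Conclusion.** The mismatch for tumor size holds. For patients imaged yearly, about 50 to 55% of patient-windows are empty, neighbouring columns rest largely on different patients, the complete-values analysis has essentially nobody in it, and the worst-value analysis imputes about half of its data. Annual windows bring the empty share to about 0 to 13%.

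The structural part, at most about half of the windows filled, needs only a yearly imaging cycle and the SAP's own limits. The percentages also need the assumed baseline scan age, timing scatter and absence of dropout. If sites in fact image more often than Table 3-1 suggests, the windows fill better and the problem shrinks. Bias from prompted or stopping scans remains a possible risk of unknown size and direction.

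This concerns one descriptive secondary endpoint. It does not touch the primary safety analysis. It is worth correcting because two pre-specified sensitivity analyses are uninformative for tumor size as written.

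**What to change.** 1. In SAP 8.2.1.6 and Table 6-3, give tumor size its own annual windows: Month 12 = Days 183-548, Month 24 = Days 549-913, Month 36 = Days 914-1187. The existing rule of taking the scan closest to target then favours the routine scan.
2. Use these windows in the by-window summary, the mixed model and both sensitivity analyses.
3. Keep the Last value on treatment row. List scans before Day 183 separately, flag End of Treatment scans, and report n per window.
4. Leave the Month 1, 3 and 9 windows for ACTH and lipids as they are.

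**Cost.** SAP wording and one window derivation; no new data collection. There would be no separate Month 6, 18 or 30 tumor column, and timing within each window would be coarser, up to about six months either side of target. Where a patient has more than one scan in an annual window, only the one closest to target enters the summary.
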